### 3.3.5. Variables (Including Exposures and Outcomes)

Table 1 presents the study variables and operational definitions.

Table 1. Variables and Definitions

Variable	Source	Definition
Cohort: Forteo-Exposed and Unexposed comparators	Commercial pharmacy claims	
 
Patients treated with Forteo (Exposed):         
 
Patients aged ≥18 years with dispensed prescription of Forteo during the cohort entry window (first observed will define the index date) (for National Drug Code [NDC] list see Table 2 in Attachment 1)
 
Forteo cohort drug utilization
 
Date of prescription fill, days of supply, quantity dispensed, dosage form and strength
 
General Population Comparator:

Baseline Characteristics:	Commercial pharmacy claims and state cancer registry files	Tables will be reported stratified for the Forteo-exposed and the comparator cohort. Baseline characteristics will include:  Age  Overlapping age groups (18+; 40+; and 65+)  Mutually exclusive age groups (18-19, then 5-year intervals thereafter, ending with 80+)  Sex  'Messection Female; which will be reported on a state or higher level (Census Division or Region level).  Payer type  Commercial plans, Medicare, Medicaid, other third parties (for example, military), and self-pay/cash payments  Dates  Month and year of cohort entry, dispensed prescription for both Forteo users and the matched cohort  Select prescription drugs dispensed during the baseline period. National drug codes collapsed to drug class groups  Therapeutic class  Count of unique dispensed prescriptions during the same month/year as Forteo grouped by therapeutic class
Outcomes: Osteosarcoma diagnosis	State cancer registry	12 ICD-O-3 codes reported in Table 1 in Attachment 1

# 3.4. Plan of Analysis

This is an exact-matched cohort design to compare the incidence of osteosarcoma among a Forteo-exposed cohort to unexposed cohorts matched at baseline. Forteo-treated patients will be matched during the same month/year as the index period using age group (5-year age categories), sex, geography (zip code), payer type (Medicare, Medicaid, commercial plans, other third

parties, and self-pay/cash payments), and count of unique dispensed prescriptions grouped by therapeutic class to the unexposed cohort during the same month/year.

Matching criteria may be adjusted if the matching ratio cannot be achieved. If matching cannot be achieved for a particular matching variable, that variable will be dropped from the matching process and controlled for in the IRR analysis (if deemed necessary).

Baseline characteristics will be measured during the look-back period and will involve prescription use other than Forteo. Quantifying the number of unique prescriptions grouped by therapeutic class during the baseline period will be used as a proxy for measuring overall health status and the presence of other chronic comorbidities.

Evaluation of the standardized mean difference between the samples' characteristics postmatching (target of <10% for good balance) will be employed. If matching was determined based on these criteria to not be well-balanced, then a logistic regression analysis could be conducted to further adjust for potential bias of characteristics and provide an estimated proportion of patients that develop osteosarcoma.

Baseline characteristics will be reported in total and stratified by reporting age categories. The number and percent of patients along with descriptive statistics (mean, standard deviation, median, 25th and 75th percentiles) will be reported for continuous data. Categorical variables (for example, payer type) will report the number and percent of patients.

Matched pairs will be statistically compared between the Forteo-exposed and the comparator cohorts pre- and postmatching. Pearson's chi-square tests, using Yate's correction for 2x2 tables, will be conducted for categorical variables and Welch Two Sample 2-sided t-tests for differences in means, assuming unequal variances. Statistical analyses will be conducted using SAS® and/or the Comprehensive R Network® using a statistical significance level of 0.05. Counts of less than 5 will be reported as "N<5" within study results.

Incidence will be estimated in the Forteo-exposed cohort as well as in the unexposed/comparator cohorts. An IRR and 95% CI will be estimated to compare the incidence of osteosarcoma among Forteo-exposed with the incidence of osteosarcoma in the matched comparator cohorts. If after the linkage there is a match, cases will be described.

Data-driven sensitivity analyses are planned. The need for data-driven sensitivity analyses will be driven by the number of identified osteosarcoma cases (for example, if there are few to no cases, there is likely little need for sensitivity analyses) and/or a qualitative assessment (for example, assessment of patient characteristics). If needed, these proposed secondary sensitivity analyses will provide another dimension to the study and will add to the robustness of the overall interpretation of study findings.

### 3.4.1. Methods

Incidence rate and IRR for osteosarcoma will be estimated among Forteo users versus matched comparator cohorts. For the primary analysis of each linkage, the IRR and 95% CI for osteosarcoma occurrence in Forteo users and nonusers will be estimated using exact conditional Poisson regression. The following describe components of the IRR:

- Incidence of osteosarcoma among the Forteo cohort will be estimated as the number of
  Forteo-exposed with a diagnosis of osteosarcoma during the study period divided by total
  person-years of follow-up where follow-up among Forteo-exposed is adjusted for
  mortality.
- 2) Incidence of osteosarcoma among the comparator cohorts will be estimated as the number of matched comparators with a diagnosis of osteosarcoma during the study period divided by the total person-years of follow-up among matched comparators where follow-up is adjusted for mortality.
- An IRR will be estimated as the incidence of osteosarcoma among the Forteo cohort divided by incidence of osteosarcoma among the matched comparators adjusted for mortality.

Health outcomes vary by age, and subsequently the effect of the populations' age distributions will be taken into account as mortality generally increases with age. Since mortality files will not be used, mortality adjustments using Centers for Disease Control and Prevention published rates will be applied to estimate appropriate time to censor each patient's person-years. A sensitivity analysis that includes assumptions about differential mortality between the cohorts will be conducted. This will be done by assuming up to 10% higher mortality for the Forteo cohort and by calculating the percent differential mortality that would be necessary for the IRR to be statistically significantly elevated.

All US state cancer registries will be invited to participate; however, it is expected that not all state registries will participate. As a result, the participating state cancer registries will cover only a percentage of the US population aged ≥18 years during the observation period. This will be addressed in 2 ways: 1) calculation of incidence rates and IRRs using a cohort restricted to patients in states with participating registries; 2) using a coverage fraction that represents the percentage of osteosarcoma cases captured in this study (based on cancer registry participation) divided by the total number of osteosarcoma cases expected. This will involve a recalculation of the person-time at risk using the exposure information for only those patients from the states with participating registries and comparing it with the proposed person-time calculation using the coverage fraction to see if they differ in a meaningful way, and repeating the IRR analysis for comparison with the IRR analysis not using the coverage fraction.

The observation period, or the time at risk, will be defined as the time postentry into the study cohort. Person-time will be calculated from the start of the observation period until the end of the study period, the linkage date, which will then be mortality adjusted and multiplied by the coverage fraction based on the participating registries. For patients with an osteosarcoma diagnosis, the observation period will begin the day after the index date and will end at the date of osteosarcoma diagnosis rather than the linkage date.

Cohorts will be selected prior to linking to registry data. If a Forteo-exposed patient is identified as having a registry identified diagnosis of osteosarcoma prior to the index date, this patient as well as their matched comparators will be removed from the study. If a Forteo-matched comparator is identified as having a registry identified diagnosis of osteosarcoma prior to the

index date, the comparator alone will be dropped from the analysis and a substitute comparator will be selected.

Descriptive characteristics will be reported for both the Forteo-exposed and comparator cohorts (See Table 1). Among the Forteo cohort, drug utilization patterns will be reported including the number of dispensed prescriptions, mean days of supply, dosage form and strength. Baseline characteristics will be reported in total and stratified by reporting age categories. The number and percent of patients along with descriptive statistics (mean, standard deviation, median, 25th and 75th percentiles) will be reported for continuous data. Categorical variables (for example, payer type) will report the number and percent of patients. Baseline characteristics reported in Table 1 will be summarized for both cohorts.

Two time periods are included with variable look-back windows for assessment of osteosarcoma diagnosis postcohort entry using a data-driven approach. Additionally, 2 comparator cohorts will be established and analyzed. The analysis will be conducted using the following scenarios:

- Primary time period: Using the full 10 years of data available for Forteo exposure and the matched cohort. This will be January 2005 through December 2 years prior to the linkage. State cancer registry data will be linked to all data during this window. This approach assesses all available data and provides a more comprehensive analysis.
- Secondary time period: Using a data-driven approach, a sensitivity analysis will be conducted. This sensitivity analysis will include a variable look-back window where the exposed cohort will only be included when at least a 3-month look-back period is available prior to the index date to describe baseline characteristics.

Findings from these analyses will be described and compared.

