### 3.3.4. Time Periods

This study will include linkages between commercial pharmacy claims data and state cancer registry data. A linkage is expected to occur late in 2016 or early in 2017 and will include data from 01 January 2005 through December 2 years prior to the linkage year.

An IRR will be estimated assessing osteosarcoma among patients treated with Forteo compared to a general population control group and an osteoporosis-treated control group. Possible differential mortality between the cohorts will be considered in a sensitivity IRR analysis.

The outcome, osteosarcoma, will be identified using 12 identified ICD-O-3 codes in state cancer registry data (See Table 1 in Attachment 1). These codes are currently used for the prospective US Forteo Patient Registry (GHBX [2]).

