### 3.3.4.2. Linkage

The linkage will include a cohort of Forteo users and matched comparators with qualifying dispensed pharmacy claims from 01 January 2005 through December 2 years prior to the linkage year. A deterministic data linkage method will be used to match on demographic variables across the commercial claims study cohorts and cancer registry data. The state cancer registry data will extend through December 2 years prior to the linkage year to account for the 9- to 18-month lag in data collection and reporting among state cancer registries in the year of the linkage. The index date will be the date of the earliest identified dispensed prescription for Forteo and the comparators will have a dispensed prescription during the same calendar month and year.

For optional sensitivity analyses, an attempt will be made to link all study cohorts to the PharMetrics Plus database for ascertainment of medical claims representing baseline patient characteristics. The linkage rate between the LRx database and PharMetrics Plus for this patient population is expected to be very low due to the age distribution of Forteo users and the underrepresentation of the 65 and older patient population.

Analysis will be conducted looking at 2 time periods. The first time period will include all exposure and outcome data from 01 January 2005 through December 2 years prior to the linkage year. This second time period will include a baseline look-back period of at least 3 months prior to the cohort entry date and will include the 6-month lag time. The baseline period will be used to identify descriptive characteristics used for matching for each cohort.

The risk detection window will be the period of time after the index date up until the linkage completion date. Person-time will be calculated for Forteo-treated population and comparator cohorts, and an IRR for the occurrence of osteosarcoma will be calculated to compare the 2 cohorts.

A follow-up linkage, if required, will be a replication of the methods and inclusion/exclusion criteria of the first linkage.

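### Person-time runs to the linkage date, but registry cases stop at December two years before the linkage year, so absolute incidence rates calculated as written come out too low

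*Protocol*

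**What the plan says.** The protocol gives two different ends to the study period.

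**Linkage date.** In section 3.4.1 the person-time rule reads: "Person-time will be calculated from the start of the observation period until the end of the study period, the linkage date". The same paragraph ends follow-up at diagnosis for cases, in place of the linkage date, which confirms that non-cases run to linkage. Section 3.3.4.2 agrees: "The risk detection window will be the period of time after the index date up until the linkage completion date".

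**December two years before the linkage year.** Section 3.3.4.2 says of the outcome source: "The state cancer registry data will extend through December 2 years prior to the linkage year to account for the 9- to 18-month lag". Cohort entry uses "qualifying dispensed pharmacy claims from 01 January 2005 through December 2 years prior to the linkage year". Section 3.4.1 describes the primary time period as follows: "Using the full 10 years of data available for Forteo exposure and the matched cohort" and "This will be January 2005 through December 2 years prior to the linkage".

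On timing, section 3.3.4 says: "A linkage is expected to occur late in 2016 or early in 2017". By the protocol's rule, the cut-off is then December 2014 or December 2015.

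Section 3.4.1 makes two adjustments to person-time: one for mortality, from published rates, and one for the coverage fraction, which reflects registry participation.

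**The concern.** A rate needs a numerator and a denominator that cover the same calendar time. Here the numerator closes at the registry cut-off and the denominator stays open until linkage. The coverage fraction makes up for states that do not take part, not for calendar time that no registry has supplied. Restricting the cohort to participating states leaves the gap in place too.

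Cohort incidence rates are a planned output (sections 3.4 and 3.4.1), and section 3.1 describes the aim as estimating incidence among Forteo users. Section 3.4 allows for few or no cases. The ratio would then say little, and person-years and absolute rates would carry much of the interpretation. Too many person-years push that interpretation towards reassurance. Section 3.1 also says that the findings from the linkage will help decide whether a further linkage is needed.

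**Working it through.** **Reproducing the plan's own figure.** January 2005 to December 2014 is 10 years, which matches section 3.4.1 for a 2016 linkage. A 2017 linkage gives January 2005 to December 2015, or 11 years.

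**Formula.** Rate = cases / person-years. An exact Poisson upper limit for x cases is chi-square(0.975; 2(x+1)) / (2 × person-years). Both scale with 1/person-years, so both are multiplied by

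K = (person-years to cut-off) / (person-years to linkage), and the shortfall is 1 − K.

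**Base case (assumed: uniform entry over T years, no mortality).** With a gap of g years between cut-off and linkage, mean follow-up is T/2 to the cut-off and T/2 + g to linkage.

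| Assumed linkage | T | g | Mean to cut-off | Mean to linkage | K | Shortfall |
|---|---|---|---|---|---|---|
| 1 Oct 2016 | 10 | 1.75 | 5.00 | 6.75 | 0.741 | 25.9% |
| End Dec 2016 | 10 | 2.00 | 5.00 | 7.00 | 0.714 | 28.6% |
| Early Jan 2017 | 11 | 1.00 | 5.50 | 6.50 | 0.846 | 15.4% |
| 31 Mar 2017 | 11 | 1.25 | 5.50 | 6.75 | 0.815 | 18.5% |

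**Varying the assumptions.** Entry density was uniform, or changed linearly by a factor of 2 in either direction. Annual mortality m was 0, 3% or 6%. A patient with x years available contributes (1 − exp(−mx))/m years on average, or x if m = 0. The extremes were:

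- Late 2016, smallest (more entry early, m = 6%, 1 October): 4.55/5.76 = 0.790, shortfall 21.0%.
- Late 2016, largest (more entry late, m = 0, end of December): 4.44/6.44 = 0.690, shortfall 31.0%.
- Early 2017, smallest (more entry early, m = 6%, January): 4.91/5.59 = 0.878, shortfall 12.2%.
- Early 2017, largest (more entry late, m = 0, 31 March): 4.89/6.14 = 0.796, shortfall 20.4%.

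**Check against the protocol's counts.** Section 3.3.2 gives 477,140 patients over about 11 years, an average of 477,140/11 = 43,376 a year, but only about 23,000 with a fill in 2015. This suggests falling entry. A straight line with that mean that ends at 23,000 starts at 2 × 43,376 − 23,000 = 63,752, a ratio r = 2.77. Mean entry time is T(r + 2)/(3(r + 1)) = 0.422T, so mean follow-up to the cut-off is 0.578T. Without mortality:

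- Late 2016: 5.78/7.53 to 5.78/7.78, shortfall 23% to 26%.
- Early 2017: 6.36/7.36 to 6.36/7.61, shortfall 14% to 16%.

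Both results lie inside the ranges above.

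**Illustration.** Assume 477,140 patients, full registry coverage, zero cases, linkage at the end of 2016, uniform entry and no mortality. The zero-case upper limit is 3.689/person-years. As written: 3.689/(477,140 × 7.00) = 1.10 per million person-years. With matched windows: 3.689/(477,140 × 5.00) = 1.55 per million.

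**Incidence rate ratio.** Section 3.3.4.2 has comparators enter in the same calendar month and year, so K is close to equal in the cohorts and cancels. Take 10% higher Forteo mortality, the bound in the protocol's own sensitivity analysis, with uniform entry and linkage at the end of 2016. The Forteo-to-comparator ratio of mean follow-up is 0.9906 to the cut-off and 0.9885 to linkage at 3% annual mortality, which shifts the rate ratio by a factor of 1.002. At 6% it is 0.9822 and 0.9785, a factor of 1.004.

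**The case against.** The strongest reply is that the protocol already holds the right definition. Sections 3.3.4, 3.3.4.2 and 3.4.1 all close the data at the same December, so the linkage date may be loose wording that a programmer would read correctly. In part this stands: the defect is a contradiction, and the low rates follow only if the person-time rule is applied literally. But that rule is the operative instruction for the denominator, and the linkage date appears as its end in three places, so literal use is a real prospect.

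The second reply is that the primary objective in section 3.2.1 is a comparison by rate ratio. This stands too. A reader might infer that the primary comparison is biased, but the working shows that it hardly changes.

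Three further inferences are not supported:

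- **That a planned confidence limit for the rate is wrong.** The protocol attaches a 95% interval only to the rate ratio. The point applies to any interval that happens to be reported for the rate.
- **That the rates would not be comparable with the Forteo Patient Registry or the Medicare study.** The document does not say how either ends person-time, and section 3.1 describes the protocols of the two database studies as harmonized.
- **That every non-case gains 1 to 2 years.** Patients censored for mortality before the cut-off, and comparators who start Forteo before it, gain none in that cohort.

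**Conclusion.** The concern holds for the absolute incidence rates. The direction is certain if the person-time rule is followed as written: the denominator includes time in which no case can be found. The size depends on the linkage date, the entry pattern and mortality, which the protocol does not fix. The 21% to 31% (late 2016) and 12% to 20% (early 2017) are ranges over stated assumptions, not bounds. The primary rate ratio is nearly unaffected.

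A side note concerns the cut-off itself. For an early-2017 linkage, December 2015 lies only 12 to 15 months back, inside the 9- to 18-month reporting lag that the rule is meant to allow for. A reader might conclude that the cut-off must be at least 18 months old. The protocol gives the lag as a range and does not show that the last year would be incomplete, so this calls for a check on completeness and not for a new rule.

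**What to change.** In sections 3.3.4.2 and 3.4.1, remove the linkage date and the linkage completion date as ends of follow-up, including in the sentence on cases. State one rule for all cohorts. Person-time ends at the earliest of:

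- osteosarcoma diagnosis;
- mortality-adjusted censoring;
- first Forteo fill (comparators);
- the registry data cut-off already stated, 31 December two years before the linkage year.

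A single study-wide cut-off also works for the coverage-fraction calculation, where some patients live in states without a participating registry.

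The cost is a few sentences of text and a changed end date in the program. Reported person-years fall. No cases are lost, since none can be identified after the cut-off. If the linkage falls in early 2017, ask the registries to confirm that the last diagnosis year is complete.

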### 3.3.2. Data Sources

### IMS Longitudinal Prescription (LRx) Data

The IMS Health (IMS) longitudinal prescription database (LRx) consists of patient-level dispensed prescriptions that enable patient prescription-filling behavior to be tracked across time, payers, and pharmacies. Data contributors include retail chains and independent pharmacies, specialty, mail-order, and long-term care pharmacies. The LRx captures prescriptions purchased through all methods of payment (for example, cash, Medicaid, third party). Currently, the database contains data for over 220 million unique de-identified patients and 1 million physicians. Data are consistently robust across all regions of the country, ranging from 57% coverage in the Southwest to 70% to 80% in the Mid-Atlantic region. The LRx represents >85% of all US retail prescriptions and 40% to 75% of US specialty and mail-order prescriptions (depending on therapeutic area). The IMS documents the saturation of pharmacies in LRx at the state and the Metropolitan Statistical Area (MSA) level; these internal IMS data can be used to estimate data completeness. The LRx data are available from 2005.

The database includes de-identified patient-level longitudinal data such as age, sex, zip codes, dispensed drug (through National Drug Code [NDC]), molecule, form, strength, quantity, and days' supply. All data are Health Insurance Portability and Accountability Act (HIPAA) compliant to protect patient privacy.

There are limitations to using pharmacy claims data for research purposes. Claims data are generated primarily for reimbursement purposes and not research. One such limitation is potential misclassification given that exposure is identified based on a claim for a dispensed prescription without information that confirms whether or not the patient actually used the medication. Based on market research data, 70% of new patients refill their Forteo prescription at least once, and 64% refill their prescription to cover at least 90 days. Therefore, the potential for exposure misclassification is likely to be minimal. In addition, LRx is an open source claims database with data contributed by pharmacies, not health plans. As such, the completeness of data capture is contingent upon the consistency of data contributions from pharmacies.

The patient counts for Forteo from LRx are as follows:

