### **State Cancer Registry Databases**

State cancer registry databases will be used to identify osteosarcoma cases diagnosed in the US during the years of observation. The variables of interest include demographic variables for matching and osteosarcoma diagnosis codes (See Table 1 in Attachment 1), month and year of diagnoses, and other clinical and pathological information. (See Section 3.5.2 for additional variables needed for linkage prior to analysis.) All US state cancer registries will be contacted with the target to recruit at least 25 state registries for participation in linkages. Results from an initial feasibility survey sent to 41 state cancer registries suggest that at least 60% are willing and able to participate in this effort. The recruitment and coordination with state registries will be handled within a parallel research study, under the facilitation of RTI Health Solutions.

Because of the lack of detailed, clinical diagnosis information in claims data, which use International Classification of Diseases diagnosis codes (ICD-9 and ICD-10), state cancer registries are deemed the appropriate source for osteosarcoma diagnosis information using International Classification of Diseases for Oncology, Third revision, (ICD-O-3) codes. State cancer registry data include information on cancer histology, stage at diagnosis, tumor grade, and date of diagnosis.

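### The stated person-time rule scales all follow-up by a case-based coverage fraction and names no primary denominator, so absolute incidence rates can be biased although a directly counted alternative is already planned

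*Protocol*

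**What the plan says.** Protocol section 3.4.1 (Methods) accepts that not all state registries will take part and gives two responses. The first is "calculation of incidence rates and IRRs using a cohort restricted to patients in states with participating registries". The second is "using a coverage fraction that represents the percentage of osteosarcoma cases captured in this study (based on cancer registry participation) divided by the total number" (here, all cases that would be expected). The person-time of the restricted cohort is then to be recalculated, with the stated purpose of "comparing it with the proposed person-time calculation using the coverage fraction to see if they differ in a meaningful way", and the IRR analysis is to be repeated without the fraction.

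The next paragraph of the same section defines time at risk. It gives one rule only: person-time runs to the linkage date, "which will then be mortality adjusted and multiplied by the coverage fraction based on the participating registries". No sentence says which of the two denominators is primary, and no threshold is given for a meaningful difference.

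Three other statements bear on this:

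- On participation, section 3.3.2 says: "Results from an initial feasibility survey sent to 41 state cancer registries suggest that at least 60% are willing and able to participate".
- On the pharmacy database (LRx), section 3.3.2 describes regional capture "ranging from 57% coverage in the Southwest to 70% to 80% in the Mid-Atlantic region".
- On location, section 3.3.2 says: "The database includes de-identified patient-level longitudinal data such as age, sex, zip codes".

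**The concern.** A case can be found only where a registry participates. The person-time that belongs with those cases is the time this cohort spent in the same states. A fraction based on osteosarcoma cases measures something else: how cases are spread over the country. The two agree only if the cohort's person-time is distributed across states as osteosarcoma cases are. Regional differences in LRx capture give a concrete reason why it may not be.

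The definition is also badly worded. Read literally, it divides a percentage by a number of cases, which does not give a fraction between 0 and 1.

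What is at stake is the absolute incidence rate. Section 3.2.1 makes incidence in treated patients part of the primary objective, and section 3.3 lists the rate beside the IRR. Section 3.4 foresees few or no cases. With no case among treated patients, the main quantitative result would be an upper limit on the rate. That limit (about 3.7 divided by person-years, two-sided 95% exact) moves in full with the denominator. Since neither denominator is named as primary, the choice could also be made after both results are known.

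**Working it through.** The protocol states no coverage fraction, incidence rate or expected number of cases, so there is no figure of its own to reproduce.

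**Formula.** Let PT be the person-time of the whole cohort, f the coverage fraction, and s the share of PT that lies in participating states.

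- Rate with the fraction = cases / (PT × f)
- Rate in the restricted cohort = cases / (PT × s)
- Relative error of the fraction-based rate = s/f − 1

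**Inputs.**

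- f: not given. The nearest figure is the feasibility survey: 60% of 41 registries is 24.6, or about 25. That is a share of registries, not of cases, so f = 0.5, 0.6 and 0.7 are assumptions.
- s: not given. As a scenario, let LRx capture be a in participating states and b in the others, with Forteo use otherwise proportional to osteosarcoma cases (an assumption). Then s = f·a / (f·a + (1 − f)·b).
- a and b: 57% and 80% as the outer values, 57% and 70% as a milder contrast, from the regional figures in section 3.3.2.

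**Worked case.** With f = 0.60, a = 0.80 and b = 0.57: s = 0.480 / (0.480 + 0.228) = 0.678, and 0.678/0.60 − 1 = +13%. With the capture values reversed: s = 0.342 / (0.342 + 0.320) = 0.517, and the error is −14%.

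| Assumed f | Capture contrast | s, lower to upper | Error of the rate |
|---|---|---|---|
| 0.50 | 57% vs 80% | 0.416 to 0.584 | −17% to +17% |
| 0.60 | 57% vs 80% | 0.517 to 0.678 | −14% to +13% |
| 0.70 | 57% vs 80% | 0.624 to 0.766 | −11% to +9% |
| 0.60 | 57% vs 70% | 0.550 to 0.648 | −8% to +8% |

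The error is zero when s = f. It is positive (rate too high) when participating states have the better capture.

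**Effect on the IRR.** The relative error is s(Forteo)/s(comparator) − 1. If both cohorts have the same state mix, it is zero. As an illustration with 3 and 10 cases and person-time of 1 to 4, the IRR is (3/1)/(10/4) = 1.20, with an exact 95% CI of 0.21 to 4.66. These values are the same whether both person-times are multiplied by 1, 0.60 or 0.69. If geography were no longer matched and the shares were, for example, 0.66 and 0.60, the IRR would be off by 0.66/0.60 − 1 = +10%.

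**The case against.** The strongest reply is that the remedy is already in the plan. The restricted cohort is the first of the two listed approaches, and the protocol promises a comparison of the two denominators. What remains could be called a question of labelling, which an analysis plan may settle. This stands in part: the restricted analysis is not missing. But the protocol does state a person-time rule, that rule uses the multiplier, and the text treats it as the proposed calculation against which the restricted one is checked.

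A second reply is that the primary comparison is an IRR and that a common multiplier cancels. This stands while matching on zip code holds, as section 3.4.2 assumes. A reader might infer that the IRR is biased as well; the documents do not support that under intact matching. The reservation is that sections 3.4 and 3.4.6 allow a matching variable to be dropped and controlled for only if judged necessary.

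Third, the size is modest. The larger errors need all participating states at one capture extreme and all others at the opposite one, and nothing in the protocol suggests such a split. Sampling error is also much larger: for 3 cases, exact Poisson 95% limits are 0.21 to 2.92 times the estimated rate. Both points are fair. Still, this bias can be avoided, and more cases would not remove it.

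Two further inferences are tempting but unsupported. One is that coverage would be deducted twice, by restricting the cohort and also multiplying. Section 3.4.1 contrasts the two calculations and refers to an IRR analysis without the fraction, so they are alternatives. The other is that restriction gives an exact denominator. It does not: follow-up is still adjusted with published mortality rates, and patients can move between states.

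**Conclusion.** The point holds for the absolute incidence rates. The operative rule relies on a fraction that need not match the cohort's person-time in participating states, the fraction is poorly defined, and no primary denominator is named. The direction of the bias is unknown. Its size runs from 0 to about 17% for assumed fractions of 0.5 to 0.7 under the outer capture contrast, and is about 8% at an assumed 0.60 under the milder one. A reader might take the top of that range as the expected error; it is a bound. These figures also assume that Forteo use follows osteosarcoma cases apart from differences in capture, which the documents do not establish. The primary IRR is not at risk while geographic matching is kept. The change is worth making because the better denominator can be counted from data already held.

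**What to change.** In section 3.4.1, name as primary the mortality-adjusted person-time of Forteo users and their matched sets whose index zip code lies in a participating state, counted directly for the years that state's registry supplied, with no coverage multiplier. Amend the observation-period paragraph to match.

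Keep the coverage-fraction version as a sensitivity analysis. Define the fraction as cases expected in participating states divided by cases expected in all states, with the same age range and calendar years in both.

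Both analyses are already planned, so the change is mainly one of order and wording. The reported cohort becomes smaller. Almost no case is lost, since cases can be found only in participating states; the exception is a patient who moved into one after the index date. Moves between states remain a small source of error.
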